# SYNOPSIS

Protocol Title:	A Multi-Center Randomized, Double-Masked, Parallel Design, Vehicle-Controlled Phase 2 Clinical Trial to Assess the Efficacy and Safety of 0.25% -Reproxalap Ophthalmic Solution Compared to Vehicle in Subjects with Dry Eye Disease
Protocol Number:	ADX-102-DED-024
Investigational Product:	0.25% Reproxalap Ophthalmic Solution (reproxalap)
Study Phase:	2
Primary Objective(s):	To evaluate the efficacy of reproxalap, as assessed by conjunctival redness, Schirmer's Test, and ocular dryness after dosing prior to and during exposure to the Controlled Adverse Environment ® (CAE) in subjects with dry eye disease
Overall Study Design:	

Structure:	Multi-center, double-masked, randomized parallel design trial	
Duration:	An individual subject's participation is estimated to be approximately 16-32 days.	
Controls:	Vehicle Ophthalmic Solution (vehicle)	
Dosage/Dose Regimen:	Test article (reproxalap or vehicle) will be dosed topically in both eyes. Test article will be administered QID on Day 1 (Visit 2). On Day 2 (Visit 3), test article will be administered once	
Summary of Visit Schedule:	
 
Three visits over the course of approximately 2 weeks:
 
Visit 1 = Day -14 -16/+2, Screening
 
	
	• Visit 2 = Day 1, Randomization/Baseline	

	• Visit 3 = Day 2 CAE ® & Study Exit
	Subjects will be randomized 1:1 to receive either reproxalap or vehicle.
Measures Taken to Reduce Bias:	ADX-102-DED-024 is a randomized treatment assignment, double-masked trial.

	assignment, double-masked trial.
Study Population Characteristics:	
Number of Subjects:	Approximately 150 subjects are expected to be enrolled in the trial.
Condition/Disease:	Dry Eye Disease (DED)
Inclusion Criteria:	
 
Subjects must meet all of the following criteria: 
 
18 years of age (either gender and any race);
 
 
 
Ability to provide written informed consent and sign the Health Information Portability and Accountability Act (HIPAA) form;
 
Reported history of dry eye for
 
Reported history of use or desire to use eye drops for dry eye symptoms
 
Corneal fluorescein staining sum
 

Exclusion Criteria:	Subjects must not meet any of the following criteria: 1. Clinically significant slit lamp findings

# 12. Pregnancy, nursing, or planned pregnancy during the conduct of the trial;

- 13. Unwillingness to submit a urine pregnancy test at Visit 1 and Visit 3 (or early termination visit) if of childbearing potential. (Non-childbearing potential is defined as a woman who is permanently sterilized [e.g., has had a hysterectomy or tubal ligation], or is postmenopausal [without menses for 12 consecutive months]);
- 14. If of childbearing potential (female or male), unwillingness to use an acceptable means of birth control. (Acceptable methods of contraception include: hormonal – oral, implantable, injectable, or transdermal contraceptives; mechanical – spermicide in conjunction with a barrier such as a diaphragm or condom; intrauterine device [IUD]; or surgical sterilization of partner. For nonsexually active males or females, abstinence may be regarded as an adequate method of birth control; however, if the subject becomes sexually active during the study, he/she must agree to use adequate birth control as defined above for the remainder of the trial.);
- 15. Known allergy and/or sensitivity to the test article or its components;
- 16. A condition that the investigator feels may put the subject at significant risk, may confound the study results, or may interfere significantly with the subject's participation in the trial;
- 17. Current enrollment in an investigational drug or device study or have used an investigational drug or device within 30 days of Visit 1;
- 18. Use of reproxalap ophthalmic solution in the past year;

	19. Current use of any medication
	20. Inability or unwillingness to follow instructions, including participation in all study assessments and visits.
Study Formulations and Formulation Numbers:	0.25% Reproxalap Ophthalmic Solution
Evaluation Criteria:	
	Conjunctival redness     in CAE
Primary Endpoint:	Visual analog scale eye dryness score
	Schirmer's Test change from baseline
	Visual analog scale eye dryness score
	• Ora Calibra ® Ocular Discomfort Scale
	Ocular Discomfort & 4-Symptom Questionnaire
	• Ora Calibra ® Conjunctival Allergen Challenge
	Ocular Itching Scale
	Conjunctival Redness
	Change in tear RASP levels
Exploratory Endpoints	• Conjunctival redness, Ora Calibra ® Ocular Discomfort Scale, and visual analog scale dryness
Safety Endpoints:	Visual acuity     Slit-lamp evaluation

• Adverse event query     • Intraocular Pressure (IOP)
Dilated fundoscopy

General Statistical Methods and Types of Analyses:

Statistical analyses will be detailed in the statistical analysis plan (SAP), which will dominate any statistical language herein. Any changes to protocol stated analyses will also be detailed in the SAP.

Sample Size:

Multiplicity Considerations:	
Multiplicity Considerations.	
	0.001
	0.001

Primary Efficacy Analyses:

Safety Analyses:	
Summary of Known and Potential Risks and Benefits to Human Subjects:	
Refer to Investigator's Brochure.	

# List of Abbreviations

AE	adverse event
CAE	Controlled Adverse Environment®
CFR	Code of Federal Regulations
DED	dry eye disease
DES	dry eye syndrome
DHHS	Department of Health and Human Services
ETDRS	Early Treatment of Diabetic Retinopathy Study
FDA	Food and Drug Administration
GCP	Good Clinical Practice
HIPAA	Health Information Portability and Accountability Act
ICF	informed consent form
ICH	International Council for Harmonisation
IEC	Independent Ethics Committee
IRB	institutional/independent review board
LogMAR	logarithm of the minimum angle of resolution
Ora	Ophthalmic Research Associates, Inc.
OTC	over the counter
RASP	reactive aldehyde species
SAE	serious adverse event
μL	microliter
VA	visual acuity
VAS	Visual analog scale

# **1** INTRODUCTION

#### **STUDY OBJECTIVES** 2

To evaluate the efficacy of reproxalap, as assessed by conjunctival redness, Schirmer's Test, and ocular dryness Controlled Adverse Environment®

(CAE) in subjects with dry eye disease.

#### **CLINICAL HYPOTHESES** 3

The clinical hypothesis is that reproxalap is more effective than vehicle in reducing the signs and symptoms of DED.

# 4 OVERALL STUDY DESIGN

ADX-102-DED-024 is a Phase 2, multi-center, randomized, double-masked, parallel design, vehicle-controlled trial designed to evaluate the efficacy and safety of 0.25% Reproxalap Ophthalmic Solution compared to vehicle in subjects with dry eye disease. Approximately 150 subjects will be enrolled in the study. Male and female subjects at least 18 years of age with a subject-reported history of dry eye disease in both eyes and meeting all other eligibility criteria will be randomized to receive reproxalap or vehicle in a 1:1 ratio (approximately 75 subjects in each treatment group).

Visit 1 (Day -14 -16/+ 2): Screening	
 
Informed Consent
 
Demographics, Medical/Medication & Ocular History
 
Urine Pregnancy Testing (as needed)
 
Symptom Questionnaires, Ocular Dryness VAS, Visual Acuity
 
Ora Calibra® Conjunctival Allergen Challenge Ocular Itching Scale
 
Slit Lamp Exam with Conjunctival Redness assessment
 
In-Office vehicle dose
 
CAE exposure with Ocular Dryness VAS, Ora Calibra® Ocular Discomfort Scale, and Conjunctival Redness Assessment
 
Slit Lamp Exam
 
Ora Calibra® Corneal and Conjunctival Staining Scale
 
Schirmer's Test
 
IOP and Dilated Fundoscopy
 
			
Visit 2 (Day 1): Randomization/Baseline	
 
Medical/Medication Update: AE Query
 
Visual Acuity
 
Slit Lamp Exam
 
Symptom Questionnaires at specified time points
 
Conjunctival Redness
 
In-Office Doses (QID)
 
Tear Collection & Schirmer's Test
 
			
Visit 3 (Day 2): CAE	
 
Medical/Medication Update: AE Query
 
Urine Pregnancy Testing (as needed)
 
Visual Acuity, Slit Lamp Exam
 
Symptom Questionnaires
 
Conjunctival Redness at specified time points
 
In-Office Doses (
 
			

 
Tear Collection
 
IOP and Dilated Fundoscopy
 
Study Exit
 

---

# **5 STUDY POPULATION**

#### 5.1 Number of Subjects (approximate)

Approximately 300 subjects will be screened to enroll approximately 150 subjects across approximately 5 sites.

#### 5.2 Study Population Characteristics

All subjects must be at least 18 years of age, be of either sex and of any race, have a subject-reported history of dry eye disease, and meet all of the inclusion criteria and none of the exclusion criteria.

#### 5.3 Inclusion Criteria

#### Each subject must meet each of the following criteria:

1. 18 years of age (either gender and any race);

2. Ability to provide written informed consent and sign the Health Information Portability and Accountability Act (HIPAA) form;

- 3. Reported history of dry eye
- 4. Reported history of use or desire to use eye drops for dry eye symptoms

5. Corneal fluorescein staining sum Ora Calibra Scale at Visit 1.

6. Response to the CAE at Visit 1, as defined by:

a.	

# 5.4 **Exclusion Criteria** Each subject may not meet any of the following criteria: 1. Clinically significant slit lamp findings at Visit 1 2. Diagnosis of an ongoing ocular infection 3. Contact lens use 4. Artificial tear eye drop use 5. Previous laser-assisted *in situ* keratomileusis (LASIK) surgery 6. Cyclosporine 0.05% or 0.09% or lifitegrast 5.0% ophthalmic solution use 7. Systemic corticosteroid therapy or other immunomodulator 8. Planned ocular and/or lid surgeries 9. Temporary punctal plugs 10. Use of and unwillingness to discontinue topical ophthalmic prescriptions 11. Corrected visual acuity

- 12. Pregnancy, nursing, or planned pregnancy during the conduct of the trial;
- 13. Unwillingness to submit a urine pregnancy test at Visit 1 and Visit 3 (or early termination visit) if of childbearing potential. (Nonchildbearing potential is

defined as a woman who is permanently sterilized [e.g., has had a hysterectomy or tubal ligation], or is post-menopausal [without menses for 12 consecutive months]);

- 14. If of childbearing potential (female or male), unwillingness to use an acceptable means of birth control. (Acceptable methods of contraception include: hormonal oral, implantable, injectable, or transdermal contraceptives; mechanical spermicide in conjunction with a barrier such as a diaphragm or condom; intrauterine device [IUD]; or surgical sterilization of partner. For non-sexually active males or females, abstinence may be regarded as an adequate method of birth control; however, if the subject becomes sexually active during the study, he/she must agree to use adequate birth control as defined above for the remainder of the trial.);
- 15. Known allergy and/or sensitivity to the test article or its components;
- 16. A condition that the investigator feels may put the subject at significant risk, may confound the study results, or may interfere significantly with the subject's participation in the trial;
- 17. Current enrollment in an investigational drug or device study or have used an investigational drug or device within 30 days of Visit 1;
- 18. Use of reproxalap ophthalmic solution in the past year;
- 19. Current use of any medication
- 20. Inability or unwillingness to follow instructions, including participation in all study assessments and visits.

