#### 7.1.4 Instructions for Dispensation, Use, and Administration

- At Visit 1, qualified subjects will be assigned a vehicle kit. Subjects will use two vials from the kit for Visit 1 in-office doses. After use, vials will be placed into a zip locked bag labeled with subject's initials and screening number for accountability.
- At Visit 2, qualified subjects will be randomized and will be assigned a single kit of 2 pouch supply of Reproxalap Ophthalmic Solution 0.25% or Vehicle. Subjects will be dosed in office four times (QID) by trained site staff.
- At Visit 3, subjects will be dosed three times in-office from the same kit by trained site staff.
- Subjects will be instructed to close their eyes for two minutes after instillation.

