#### 8.1.5 Methods for Assignment to Treatment Groups:

At Visit 1 each subject who signs the informed consent will be assigned a screening number. All screening numbers will be assigned in strict numerical sequence at each site and no numbers will be skipped or omitted.

At Visit 2, a patient who meets all the eligibility criteria will be randomized to receive treatment reproxalap or vehicle in a 1:1 ratio. Patients will be assigned a randomization number and kit number via IWRS.

The site staff will dispense to the patient the study kit labeled with the corresponding kit number. Both the randomization number and the dispensed study drug kit number will be recorded on the patient's source document and eCRF.

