#### 8.3 Examination Procedures

8.3.1 Procedures to be Performed at the Study Visit with Regard to Study Objective(s)

Visit 1 (Day -14 -16/+2, Screening)

- Informed Consent and HIPAA
- Demographics
- Medical/Medication & Ocular History
- Urine Pregnancy Test (as needed)
- Symptom Questionnaires:
  - Ocular Discomfort & 4-Symptom Questionnaire
  - Ora Calibra® Ocular Discomfort Scale
  - Ocular Dryness Visual Analog Scale
  - Ora Calibra® Conjunctival Allergen Challenge Ocular Itching Scale
- Visual Acuity (ETDRS)

- Slit Lamp Biomicroscopy with Conjunctival Redness assessment
- Fluorescein Staining using the Ora Calibra® Corneal and Conjunctival Staining Scale
- Inclusion/Exclusion Criteria Review
- In-Office Vehicle Instillation by trained site staff

CAE Ex	posure		
	_		

• Slit Lamp Biomicroscopy with Conjunctival Redness assessment

- Schirmer's Test
- Intraocular Pressure
- Dilated Exam
- Schedule for Visit 2

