#### Visit 2 (Day 1, Baseline and In-Office Dosing)

- Medical/Medication Update
- Adverse Event Query
- Visual Acuity (ETDRS)
- Slit Lamp Biomicroscopy
- Symptom Questionnaires
  - o Ocular Discomfort & 4-Symptom Questionnaire
  - Ora Calibra® Ocular Discomfort Scale
  - Ocular Dryness Visual Analog Scale
  - Ora Calibra® Conjunctival Allergen Challenge Ocular Itching Scale
- Conjunctival Redness Photography
- Inclusion/Exclusion Criteria Review
- Randomization/Enrollment
- Pre-dose #1 Schirmer's Test
- In-Office Dose #1

- Post-dose #1 Schirmer's Test
- Pre-dose #2 Tear Collection
- In-Office Dose # 2
- Post-dose #2 Tear Collection

- Pre-dose #3 Tear Collection
- In-Office Dose #3
- Post-dose #3 Tear Collection
- In-Office Dose #4
- Conjunctival Redness Photography

- Symptom Questionnaires
  - Ocular Discomfort & 4-Symptom Questionnaire
  - Ocular Discomfort
  - Ocular Dryness Visual Analog Scale
  - Ora Calibra® Conjunctival Allergen Challenge Ocular Itching Scale

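### No urine pregnancy test is required at Visit 2 before randomised dosing; the last required result is then nominally 14 days old (window 12 to 30), and the next test follows four doses

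*Protocol*

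**What the plan says.** Protocol Section 5.4, criterion 12, excludes "Pregnancy, nursing, or planned pregnancy during the conduct of the trial". Criterion 13, worded alike in Section 5.4 and the synopsis, sets the testing visits through the exclusion "Unwillingness to submit a urine pregnancy test at Visit 1 and Visit 3 (or early termination visit) if of childbearing potential".

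The Section 4 design table and the Section 8.3.1 procedure lists agree with criterion 13. The urine test appears, to be done as needed, under Visit 1 and Visit 3. Neither the Section 4 entry nor the Section 8.3.1 list for Visit 2 contains it.

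Eligibility is nevertheless applied at Visit 2. Section 8.1.5 says "At Visit 2, a patient who meets all the eligibility criteria will be randomized", and the Visit 2 list in Section 8.3.1 has an "Inclusion/Exclusion Criteria Review" immediately before randomisation. Dosing follows the same day; for Visit 2, Section 7.1.4 says "Subjects will be dosed in office four times (QID) by trained site staff". At Visit 3 the urine test is listed ahead of that day's first dose.

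Section 8.4.1 sends the reader to Appendix 1 for the schedule. The contents of Appendix 1 and of SAP Table 2 are not visible in the public documents.

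**The concern.** The test is scheduled where it cannot support the decision that depends on it. Pregnancy is an exclusion that must be satisfied when the subject is randomised at Visit 2, but no current result is required at that point. At Visit 1 the test is listed before the in-office vehicle dose, so the vehicle-only exposure has a same-day result behind it. Randomised dosing, where half the subjects are allocated to reproxalap, relies on the screening result.

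A conception too early to detect at Visit 1 could be detectable by Day 1. Such a woman would be randomised, given four doses, and test positive the next morning. Under the pregnancy rule in Section 8.3.1 (early termination) she would then be discontinued and her pregnancy followed to outcome. The same test one day earlier would have made her a screen failure with no randomised exposure.

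**Working it through.** **Inputs**

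- Visit 1 is Day -14 with a window of -16/+2 days (Protocol 8.3.1; SAP 4.1, Table 1).
- Day 1 is the day of randomisation and there is no Day 0 (SAP 4.1). Day -k is therefore k days before the first randomised dose.
- Day 1 dosing is four times, in the clinic (Protocol 7.1.4 and synopsis).
- The Visit 3 test is on Day 2 and is listed before that day's first dose (Protocol 8.3.1).

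**Check of the day count against the stated durations.** Calendar days from Visit 1 through Day 2, counting both ends, are k + 2.

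| Visit 1 | k | Days of participation, k + 2 |
|---|---|---|
| Earliest, -14 - 16 = Day -30 | 30 | 32 |
| Nominal, Day -14 | 14 | 16 |
| Latest, -14 + 2 = Day -12 | 12 | 14 |

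The synopsis gives approximately 16 to 32 days, which reproduces the nominal and the earliest rows but not the 14-day minimum. Section 8.7 gives approximately 2 to 4 weeks (14 to 28 days), which covers the minimum and the nominal but not 32. Both are approximate and neither confirms the whole range, so the result below rests on the visit window.

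**Age of the last required result at the first randomised dose.** This equals k: 30 days at the earliest screening, 14 nominally, 12 at the latest. By Day 2, when the next test is due, the screening result is k + 1 days old: 31, 15 or 13.

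**Randomised doses before the next required test.** Four. The synopsis and Section 7.1.4 differ on Day 2 dosing (once against three times), but the Day 2 test precedes any Day 2 dose, so the count does not change.

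**With a test at Visit 2 before randomisation.** The last required result would be 0 days old at the first randomised dose, and no randomised dose would precede it.

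**Other safeguards in the readable text**

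- Visit 2 medical update and criteria review: these rely on what the woman knows and reports.
- Criterion 14: excludes unwillingness to use contraception; the readable text sets no period of use before Visit 1.
- Criterion 16: leaves room for investigator judgement.
- Section 8.4.2: allows a urine pregnancy test at an unscheduled visit but does not require one.
- The pregnancy rule in Section 8.3.1: acts once a pregnancy is reported or a test is positive.

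None of these is a required test before the first randomised dose.

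**The case against.** The readable sections are consistent with one another, and nothing promises a Visit 2 test, so this can be called a deliberate choice. Whether a result about two weeks old is acceptable depends on the reproductive risk of a topical 0.25% solution; for risks the protocol refers to the Investigator's Brochure, which is not available here. The remaining gap is narrow: a pregnancy that becomes detectable between Visit 1 and Day 1, despite the contraception criterion, and is unknown to the woman at Visit 2. Its consequence is four topical doses on one day. Thirty days is a limit of the window, and the synopsis describes three visits over about two weeks.

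Most of this stands. The event is rare, no frequency or harm can be estimated, and the nominal 14 days describes the expected case better than 30. The unseen schedule tables could list a Visit 2 test, although that would contradict criterion 13 and both readable Visit 2 lists, which would then need correction.

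None of it supplies a reason to test on Day 2 and not on Day 1. Consistency across sections shows that the schedule was carried through, not that it serves an exclusion applied at Visit 2. The objection does bear on the choice of remedy: dropping the Visit 3 test altogether is harder to defend than adding one at Visit 2.

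**Conclusion.** The concern holds as a low-cost safety improvement worth considering. In the readable text no urine pregnancy test is required before randomised dosing. The last required result is nominally 14 days old at the first randomised dose, with a range of 12 to 30 days, and four randomised doses precede the next test.

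This assumes that Appendix 1 and SAP Table 2 match criterion 13 and the visit lists, and that the SAP's day numbering applies to the protocol's window. The matter is too rare to have a material effect on alpha, power or the primary analysis. The documents shown give neither the number of women of childbearing potential nor any reproductive-risk information, so no case count or size of harm is claimed.

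**What to change.** Require a negative urine pregnancy test at Visit 2, before randomisation, for women of childbearing potential. Amend criterion 13 (Section 5.4 and synopsis), the Section 4 table, the Visit 2 list in Section 8.3.1, and Appendix 1 and SAP Table 2 if they do not already show it.

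- **Preferred: add Visit 2 and keep Visit 3.** Nothing is lost. The cost is one extra urine test per woman of childbearing potential.
- **Alternative: move the Visit 3 test to Visit 2 and keep the early-termination test.** This adds no procedure, but completers lose their only scheduled test after randomised dosing starts. A Day 2 test should add little to one done the day before; that is a judgement, not something the documents state.

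Under either option, the Visit 2 test prevents exposure only for pregnancies already detectable on Day 1. No new SAP output is needed, because Listing 16.2.8.5 already covers pregnancy tests for all female screened subjects.

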#### 5.5 Withdrawal Criteria (if applicable)

Subjects may voluntarily withdraw from the trial at any time. Additionally, subjects may be discontinued for safety reasons as determined by the investigator and/or Medical Monitor.

# **6 STUDY PARAMETERS**

#### 6.1 **Primary Endpoint**

- Conjunctival redness
- Visual analog scale eye dryness score
- Schirmer's Test

### 6.2 Safety Endpoints

- Visual acuity
- Slit-lamp evaluation
- Adverse event query
- Intraocular Pressure (IOP)
- Dilated fundoscopy

### 6.3 Secondary Endpoints

- Visual analog scale eye dryness score
- Ora Calibra® Ocular Discomfort Scale
- Ocular Discomfort & 4-Symptom Questionnaire
- Ora Calibra® Conjunctival Allergen Challenge Ocular Itching Scale
- Conjunctival redness

### 6.4 Exploratory Endpoints

- Change in tear RASP levels
- Conjunctival redness, Ora Calibra® Ocular Discomfort Scale, and visual analog scale dryness score

# 7 STUDY MATERIALS

#### 7.1 Study Treatment(s)

7.1.1 Formulations

Randomized Study Treatments

- 0.25% Reproxalap Ophthalmic Solution
- Vehicle
- 7.1.2 Study Drug Packaging Configuration

For Visit 1 only, vehicle vials are packaged in 5-count pouches, which will then be packaged into kits. These kits will be made of 2 of the 5-count pouches.

Study drug and vehicle vials are packaged in 5-count pouches, which will then be packaged into kits that will supply for the study duration. These kits will be made of 2 of the 5-count pouches.

#### 7.1.3 Study Drug Storage and Accountability

The study drug must be stored in a secure area accessible only to the investigator and his/her designees. The study drug will be administered only to subjects entered into the clinical study, in accordance with the conditions specified in this protocol.

The study drug is to only be prescribed by the principal investigator or his/her named sub investigator(s), and is to only be used in accordance with this protocol. The study drug must only be distributed to subjects properly qualified under this protocol to receive study drug. The investigator must keep an accurate accounting of the study drug by maintaining a detailed inventory. This includes the amount of study drug received by the site, amount dispensed to subjects, amount returned to the site by the subjects, and the amount returned to the Sponsor upon the completion of the study.

